For efficacy analysis derived from on-site visit assessments (e.g., BSA, IGA, EASI, 5-D Pruritus Scale, POEM), Baseline is defined as the most recent measurement prior to the first administration of study drug (i.e., assessment at the Baseline visit on Day 0 per protocol or relative study Day 1).

For the rescue medication diary, the Baseline rescue medication days is the number of rescue medication days recorded during the 2 weeks (Day -14 to Day -1) prior to the Baseline visit.

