6.5.6 Rescue Medication During Treatment Period

The treatment period (also referenced as "on-treatment") begins on date of subject's first dose and ends on Day of Visit 4 - 1, even if the subject has applied IP on Day of Visit 4.

Based on recorded use of rescue medication the following variables will be derived and normalized as described in section 7.5.4 for all subjects:

- Number of days in a month with rescue treatment (for Week 1 to Week 4 and Week 5 to Week 8)
- Number of days every 2 weeks with rescue treatment (for Day -14 to -1 for Baseline, Day 1 to Day of Visit 3 -1 for Week 2, Day of Visit 3 to Day of Visit 4 -1 for Week 4, Day of Visit 4 to Day of Visit 4 + 13 for Week 6, and Day of Visit 4 + 14 to Day of Visit 5 1 for Week 8)

Proportion of subjects with rescue treatment, and the above two variables (number of days in a month with rescue treatment and number of days every 2 weeks with rescue treatment) will be derived and normalized for subjects with recorded use of rescue medication.

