7.5.4 Rescue Medications

The number of rescue medication days during the treatment period will be compared to the number of rescue medication days during the 2-week washout period (Day -14 to -1) using:

- 4-week treatment period:
 - Day 1 to Day of Visit 4 1 for all 4 weeks of treatment (Weeks 1 4)
- 2-week intervals of the treatment period:
 - Day 1 to Day of Visit 3-1 for first 2 weeks of treatment (Weeks 1-2)
 - Day of Visit 3 to Day of Visit 4 1 for last 2 weeks of treatment (Weeks 3 4)
- 4-week follow-up period:
 - Day of Visit 4 to Day of Visit 5 1 for all 4 weeks of follow-up (Weeks 5 8)
 - 2-week intervals of the follow-up period:
 - Day of Visit 4 to Day of Visit 4 + 13 for first 2 weeks of follow-up (Weeks 5 6)

Protocol: PRB244-01 STATISTICAL ANALYSIS PLAN Confidential

Version 3.0 12-Jan-22

Day of Visit 4 + 14 to Day of Visit 5 - 1 for last 2 weeks of follow-up (Weeks 7 - 8)

Each time interval will be normalized as a rate using the following formula:

$$\# rescue medication \ days = \left(\frac{\# \ days \ rescue \ medications \ used \ in \ interval}{\# \ actual \ days \ in \ interval}\right) * \# \ expected \ days \ in \ interval$$

For example, if there are 30 days in the Week 4 interval (the 2 weeks between visits 3 and 4), and a subject uses rescue medications for 7 of those 30 days, then the formula will be calculated as (7/30)*14=3.27. That is, 3.27 rescue medication days should be reported for the interval covering Weeks 3 and 4.

Change in rescue medication days from Baseline to each post-baseline visit will be tabulated. Number of rescue medication days per 2-week interval and per study period (treatment, followup) will be listed.

The use of any of the allowed rescue medications in the rescue medication diary data will be counted for the rescue medication days. If multiple rescue medications are reported on a single date, that date is still counted as only 1 rescue medication day. "Other" rescue medication selected in the daily diary will be confirmed to be one of the allowed rescue medications, and only the allowed rescue medications will be included as rescue medication days while others will not (such as other concomitant medications or prohibited medications).

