Weeks 7 - 8 rescue medication days = number of rescue medication days from Day of Visit 4 + 14 to Day of Visit 5 - 1.

Weeks 5-8 total rescue medication days = number of rescue medication days from Day of Visit 4 to Day of Visit 5-1.

[2] Each time interval is normalized as a rate where (# Rescue Medication Days) = [(# Days Rescue Medications Used in Interval) / (# Actual Days in Interval)] * (# Expected Days in Interval).

[3] CFB = Change from Baseline.

[4] n = Number of subjects who have taken at least one rescue medication during that time point. N = Number of subjects with data at that time point. Statistics for Mean, SD,

Median, Min, and Max are computed for subjects who have taken at least one rescue medication during that time point.

Source: Listing XXXX PROGRAM NAME: XXXXXXXXX

Table 14.3.10 Summary of Medical History by System Organ Class and Preferred Term (Safety Population)

| | | B244 O.D. 5.0 | B244 O.D. 20.0 | Pooled B244 | Vehicle |
|---|-----------|---------------|----------------|-------------|-----------|
| | Statistic | (N=xx) | (N=xx) | (N=xx) | (N=xx) |
| Number of Subjects with at Least One MH Event [1] | n (%) | xx (xx.x) | xx (xx.x) | xx (xx.x) | xx (xx.x) |
| System Organ Class #1 [2,3] | n (%) | xx (xx.x) | xx (xx.x) | xx (xx.x) | xx (xx.x) |
| Preferred Term #1 | n (%) | xx (xx.x) | xx (xx.x) | xx (xx.x) | xx (xx.x) |
| Preferred Term #2 | n (%) | xx (xx.x) | xx (xx.x) | xx (xx.x) | xx (xx.x) |
| Preferred Term #3 | n (%) | xx (xx.x) | xx (xx.x) | xx (xx.x) | xx (xx.x) |
| etc. | | | | | |
| System Organ Class #2 | n (%) | xx (xx.x) | xx (xx.x) | xx (xx.x) | xx (xx.x) |
| Preferred Term #1 | n (%) | xx (xx.x) | xx (xx.x) | xx (xx.x) | xx (xx.x) |
| Preferred Term #2 | n (%) | xx (xx.x) | xx (xx.x) | xx (xx.x) | xx (xx.x) |
| Preferred Term #3 | n (%) | xx (xx.x) | xx (xx.x) | xx (xx.x) | xx (xx.x) |
| etc. | | | | | |

[1] Percentage and all subsequent percentages based on the number treated.
[2] Subjects will be counted once per System Organ Class/Preferred Term.
[3] MedDRA Dictionary version XX.X was used to code medical history events.
Source: Listing XXXX
PROGRAM NAME: XXXXXXXXX

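### Table 14.3.9.2 computes change in rescue days only in subjects using rescue in that same interval, so stoppers drop out, starters stay, and the mean change is biased upward

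*SAP*

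**What the plan says.** Baseline for rescue use is a 14-day count: SAP 6.4 takes the days with rescue from Day −14 to Day −1.

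SAP 6.5.6 derives the rescue-day variables twice: once for all subjects, and once more, where they "will be derived and normalized for subjects with recorded use of rescue medication". It does not say when that use must have occurred.

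The shells follow this split. Table 14.3.9.1 covers all subjects in the Safety population, and Table 14.3.9.2 covers users. Both have change-from-baseline rows for Weeks 1–2, 3–4, 5–6 and 7–8, and total rows without change for Weeks 1–4 and 5–8. In Table 14.3.9.2, footnote 4 hangs on the header of the Statistic column, so it governs every row. It defines the counts as "n = Number of subjects who have taken at least one rescue medication during that time point. N = Number of subjects with data at that time", and it restricts the summary statistics to users in the same interval ("Median, Min, and Max are computed for subjects who have taken at least one rescue medication during that time point").

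SAP 7.5.4 states that "The number of rescue medication days during the treatment period will be compared to the number of rescue medication days during the 2-week washout period". The intervals listed beneath include the 4-week treatment and follow-up periods. Footnote 2 of the tables normalises each interval to its own expected length ("Each time interval is normalized as a rate where (# Rescue Medication Days").

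**The concern.** Whether a subject contributes to a change row in Table 14.3.9.2 depends on the post-baseline value being summarised. A washout user who needs no rescue in Weeks 3–4, the best result on this measure, is absent from the Weeks 3–4 change. A subject with no washout use who starts rescue is present with a positive change. Selection by the outcome pushes the mean up. Because it happens after randomisation, the three arms' columns need not describe comparable subjects.

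The printed count compounds this. The change rows show only N, which footnote 4 defines as subjects with data, while the statistics beside it come from the n users. A reader would attach the mean to the wrong denominator.

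At stake is any statement in the report that topical steroid use rose or fell on treatment. The users' table and the all-subject table can disagree in sign, and the SAP does not say which one counts.

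There is also a wording problem in SAP 7.5.4. It sets 4-week counts against a 2-week count without a common scale.

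**Working it through.** **1. The plan's own figure.** The worked example in SAP 7.5.4 has 7 rescue days in a 30-day interval with 14 expected: (7/30) × 14 = 3.27. It reproduces. The normalisation formula is not the problem.

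**2. The mechanism in a constructed cohort (assumed figures).** Take 100 subjects, of whom 30 use rescue on 3 days in washout. Stoppers go to 0 days, starters go from 0 to 3, and the others do not change.

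- 10 stop, 10 start. All subjects: (10 × −3 + 10 × 3)/100 = 0.00. Current users (20 unchanged, 10 new): (20 × 0 + 10 × 3)/30 = +1.00.
- 15 stop, 5 start. All subjects: (15 × −3 + 5 × 3)/100 = −0.30. Current users: (15 × 0 + 5 × 3)/20 = +0.75.
- 15 stop, none start. All subjects: (15 × −3)/100 = −0.45. Current users: 0/15 = 0.00.

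The second case shows that the sign can reverse.

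**3. Size under simple usage models (assumed).** Let X0 be washout days and X1 later days, with means l0 and l1. For independent Poisson counts, the mean change among current users is

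E[X1 − X0 | X1 > 0] = l1/(1 − e^(−l1)) − l0.

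For stable users plus never-users, never-users have X1 = 0 and drop out. Suppose one third of subjects average 3 days per 14, giving 1 day per 14 overall. With a binomial count over 14 days, the users-only value is l1/(1 − (1 − l1/14)^14) − 3.

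| Pattern (days per 14) | True all-subject change | Users-only change |
|---|---|---|
| Poisson, 1 to 1 | 0 | 1/0.632 − 1 = +0.58 |
| Poisson, 2 to 2 | 0 | 2/0.865 − 2 = +0.31 |
| Gamma-binomial simulation, shape 0.5, mean 1 | 0 | +0.44 |
| Gamma-binomial simulation, shape 0.5, mean 2 | 0 | +0.31 |
| Stable users, 3 to 3 | 0 | 3/0.966 − 3 = +0.1 |
| Poisson, 1 to 0.5 | −0.50 | 0.5/0.393 − 1 = +0.27 |
| Stable users, 3 to 1.5 | −0.50 | 1.5/0.795 − 3 = −1.1 |

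With no true change, the bias is about +0.1 to +0.6 days per 14. In the last row the users themselves truly change by −1.5, so −1.1 is still too high for them.

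**4. A subset fixed by washout use.** With no true change the roles of X0 and X1 swap, so E[X1 − X0 | X0 > 0] is about −0.3 to −0.6 in the Poisson and gamma-binomial models. This is regression to the mean. It affects all arms alike, because membership is settled before randomisation.

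**5. Interval length.** Take a subject with 2 rescue days in every 14. Each 2-week change is 2 − 2 = 0. If the expected length of the 4-week interval is 28 days (implied, not stated), the 4-week count is (4/28) × 28 = 4 against a washout count of 2. On a 14-day scale it is (4/28) × 14 = 2, and the difference is 0.

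**The case against.** The strongest reply is that the plan already contains the unbiased display. Table 14.3.9.1 has the same change rows for all subjects, and a stopper counts there as a decrease. Table 14.3.9.2 prints the share of users in each interval, which falls when subjects stop. Its title announces a users-only table, and footnote 4 discloses the rule. Rescue days are not a primary, secondary or exploratory efficacy endpoint, and no test is planned on them. All of this stands and limits the consequence. It does not make the conditional change rows interpretable.

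It could also be said that the N in the change rows shows they were meant for everyone with data. They would then merely repeat Table 14.3.9.1, and footnote 4 says otherwise. As written, the shell cannot satisfy both.

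Three stronger readings are tempting, and the documents do not support them:

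- A reader might infer that the plan never credits stopping rescue. Table 14.3.9.1 does.
- A reader might infer that an unchanged user is tabulated as worse because 4 weeks are compared with 2. Neither shell has a change row for the 4-week totals. The mismatch is only in the text of SAP 7.5.4, and Listing 16.2.13.3 already uses different thresholds for the two lengths (3 days in washout, 7 in each 4-week period).
- A reader might infer that the users' table cannot show a benefit when use halves. In the stable-user pattern it shows −1.1.

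**Conclusion.** The point holds for the change rows of Table 14.3.9.2. They are conditional on current use, so the mean change is biased upward, and the printed N is not the number analysed. With no true change the bias is about +0.1 to +0.6 days per 14, for assumed average use of 1 to 2 days per 14. That range is not a bound: the constructed cohort, with heavier turnover, gives more (+1.00 when 10 stop and 10 start). When use truly falls, the printed change may have either sign. Whether the subset actually differs between arms cannot be known from the documents; the design simply does not prevent it.

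The reach is small. Table 14.3.9.1 is not affected, the display is descriptive, and the primary ANCOVA does not use it. In SAP 7.5.4 the defect is one of wording. The correction is worth making because it costs little and removes a table that could contradict its companion.

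**What to change.** - State in SAP 7.5.4 that the all-subject change in Table 14.3.9.1 is the basis for any statement about change in rescue use.
- In Table 14.3.9.2, either delete the change rows or define their subset by rescue use in washout (Day −14 to −1). In the second case, keep the subset fixed for all intervals, count later zeros, print the matching n, and report separately the subjects with no washout use who start later.
- If the washout-user subset is kept, say that only the difference from vehicle is to be interpreted. The named downside is that the within-arm change falls by regression to the mean, by about −0.3 to −0.6 days per 14 with no true change in the models above.
- In SAP 7.5.4, say that 4-week counts are expressed as days per 14 days before they are compared with washout. This corrects the text only, since no shell tabulates a 4-week change.

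The cost is a footnote, the shell rows and a few lines of text. No new data are needed.

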1.2 APPENDIX B: Listings

| Display Number | Title | Population |
|-------------------|---|--------------|
| Listing 16.2.1 | Subject Enrollment and Disposition | All Subjects |
| Listing 16.2.2 | Protocol Deviations (PD)/Violations (PV) | Randomized |
| Listing 16.2.3 | Subjects Excluded from the Efficacy Analysis | Randomized |
| Listing 16.2.4 | Demographic and Baseline Characteristics | Randomized |
| Listing 16.2.5.1 | Study Drug Accountability | Safety |
| Listing 16.2.5.2 | Study Drug Exposure and Treatment Compliance | Safety |
| Listing 16.2.5.3 | Study Drug Dosing and Secondary Treatment Compliance | Safety |
| Listing 16.2.6.1 | WI-NRS Daily Ratings and Weekly Averages | Randomized |
| Listing 16.2.6.2 | AI-NRS Daily Ratings and Weekly Averages | Randomized |
| Listing 16.2.6.3 | POEM Items and Score | Randomized |
| Listing 16.2.6.4 | 5-D Pruritus Scale Items and Score | Randomized |
| Listing 16.2.6.5 | IGA | Randomized |
| Listing 16.2.6.6 | EASI Items and Score | Randomized |
| Listing 16.2.7.1 | Adverse Events | Safety |
| Listing 16.2.7.2 | Adverse Event Details | Safety |
| Listing 16.2.7.3 | Adverse Events for COVID-19 | Safety |
| Listing 16.2.7.4 | Deaths | Safety |
| Listing 16.2.8.1 | Hematology Parameters | Safety |
| Listing 16.2.8.2 | Clinical Chemistry Parameters | Safety |
| Listing 16.2.8.3 | Urinalysis Parameters | Safety |
| Listing 16.2.8.4 | Urine Pregnancy Test | Safety |
| Listing 16.2.8.5 | Serology Parameters | Safety |
| Listing 16.2.9 | Patient Reported Local Tolerability | Safety |
| Listing 16.2.10 | Vitals Signs | Safety |
| Listing 16.2.11 | Physical Examination | Safety |
| Listing 16.2.12 | Smoking History | Safety |
| Listing 16.2.13.1 | Prior and Concomitant Medications | Safety |
| Listing 16.2.13.2 | Rescue Medications | Safety |

| Listing 16.2.13.3 | Rescue Medication Days | Safety |
|-------------------|-----------------------------|--------|
| Listing 16.2.14 | Medical History | Safety |
| Listing 16.2.15.1 | COVID-19 Test Results | Safety |
| Listing 16.2.15.2 | COVID-19 Missed Assessments | Safety |

Listing 16.2.1 Subject Enrollment and Disposition (All Subjects)

| | | | | Date of Study Completion | 1 |
|---------------|-------------------|------------------|-----------------|--------------------------|----------------------------|
| Subject ID | Treatment | Study Population | Disposition | or Discontinuation | Reason for Discontinuation |
| XXXXXX | N/A, | N/A, | Screen Failure, | DDMMMYYYY | XXXXXXXX |
| | B244 O.D. 5.0, | Safety, | Enrolled, | | |
| | B244 O.D. 20.0, | mITT, | Completed, | | |
| | Vehicle | PP | Discontinued | | |
| Source: SDTM. | XXXX or ADaM.XXXX | | | | |
| PROGRAM NA | ME: XXXXXXXXXX | | | | DATE: HH:MM/DDMMMYYYY |

Listing 16.2.2 Protocol Deviations (PD) / Violations (PV) (Randomized Subjects)

| Subject ID | Treatment | Date of Deviation | Deviation Grade | Deviation Category | Deviation Description |
|---------------------------|--|-------------------|-----------------|--------------------|-----------------------|
| XXXXXX | N/A, B244 O.D. 5.0, B244 O.D. 20.0, Vehicle | DDMMMYYYY | Major, Minor | XXXXXXXX | XXXXXXXX |
| Source: SDTM PROGRAM N | .XXXX or ADaM.XXXX AME: XXXXXXXXXXX | | | | DATE: HH:MM/DDMMMYYYY |

Listing 16.2.3 Subjects Excluded from the Efficacy Analysis (Randomized Subjects)

| Subject ID | Treatment | Safety Population | mITT Population | PP Population | Reason for Exclusion |
|--------------|--|-------------------|-----------------|---------------|---|
| xxxxxx | N/A, B244 O.D. 5.0, B244 O.D. 20.0, Vehicle | Yes, No | Yes, No | Yes, No | No IP Applied, No Post-Baseline Evaluation Visit, Major Protocol Deviation, Did Not Complete Week 4 Visit, |
| Source: SDTM | M.XXXX or ADaM.XXX | XX | | | Applied <50% IP |

PROGRAM NAME: XXXXXXXXXX

Listing 16.2.4 Demographic and Baseline Characteristics (Randomized Subjects)

| | | Age | | | | | Rescue Medication | | |
|--------------|--|---------|--------|------------------------|--|----------------|-------------------|--|--|
| Subject ID | Treatment | (Years) | Sex | Ethnicity | Race | Smoking Status | Days [1] | | |
| XXXXXX | N/A, | XX | Male, | Hispanic or Latino, | American Indian or Alaska Native, | Yes, | XX | | |
| | B244 O.D. 5.0, | | Female | Not Hispanic or Latino | Asian, | No | | | |
| | B244 O.D. 20.0, | | | | Black or African American, | | | | |
| | Vehicle | | | | Native Hawaiian or Other Pacific Islander, | | | | |
| | | | | | White, | | | | |
| | | | | | Other (Specify) | | | | |
| [1] Number o | 1] Number of days during the washout period (Days -14 to -1) that rescue medications were taken. | | | | | | | | |

Source: SDTM.XXXX or ADaM.XXXX PROGRAM NAME: XXXXXXXXX

Listing 16.2.5.1 Study Drug Accountability (Safety Population)

| | | Kit | Kit | Lot | Visit/ | Visit/ | Weight | Weight |
|------------|-----------------|--------|-------|--------|----------------------|--------------------|---------------|--------------|
| Subject ID | Treatment | Number | Label | Number | Date Dispensed | Date Returned | Dispensed (g) | Returned (g) |
| XXXXXX | N/A, | 1 | XXXXX | XXXXX | Baseline / DDMMMYYYY | Week X / DDMMMYYYY | XX.X | XX.X |
| | B244 O.D. 5.0, | 2 | XXXXX | XXXXX | Baseline / DDMMMYYYY | Week X / DDMMMYYYY | XX.X | XX.X |
| | B244 O.D. 20.0, | 3 | XXXXX | XXXXX | Week 2 / DDMMMYYYY | Week X / DDMMMYYYY | XX.X | XX.X |
| | Vehicle | | | | | | | |

Source: SDTM.XXXX or ADaM.XXXX PROGRAM NAME: XXXXXXXXXX

| Subject ID | Treatment | Total Weight Dispensed (g) | Total Weight Returned (g) | Net Weight (g) [1] | 50% IP Applied [2] | Compliance (%) based on Weight [3] |
|------------|---|-------------------------------|------------------------------|--------------------|--------------------|--|
| XXXXXX | N/A, B244 O.D. 5.0, B244 O.D. 20.0, Vehicle | XX.X | XX.X | XX.X | Yes, No | XX.X |

Listing 16.2.5.2 Study Drug Exposure and Treatment Compliance (Safety Population)

[1] Net Weight of Study Drug (g) = (Total Weight Dispensed (g)) – (Total Weight Returned (g)).

[2] Subjects who administered at least 50% of IP (where Net Weight of Study Drug (g) is at least 50% of the initial product weight (g) (i.e., 0.14 g per pump * 20 pumps per day * 28 days = 78.4 g).

[3] Compliance (%) based on IP Weight = (Net Weight of Study Drug (g)) / (Planned Study Drug Use per Day (g) * Number of Days Expected Use of Study Drug) where Planned Study Drug Used per Day = 2.8g and Number of Days Expected Use of Study Drug = 28 days.

Source: SDTM.XXXX or ADaM.XXXX

PROGRAM NAME: XXXXXXXXXX

Listing 16.2.5.3 Study Drug Dosing and Secondary Treatment Compliance (Safety Population)

| Subject ID | Treatment | Date/Time of AM Dose [1] | Date/Time of PM Dose [1] | Record Used for Secondary Compliance [2] | Number of Dosing Diaries Entered [1] | Compliance (%) based on Diary Entries [3] |
|------------|--|--------------------------|--------------------------|---|---|--|
| XXXXXX | N/A, B244 O.D. 5.0, B244 O.D. 20.0, Vehicle | DDMMMYYYY/ HH:MM | DDMMMYYYY/ HH:MM | Yes, No | XXX | XX.X |

[1] Date/Time of AM/PM Dose is taken from the Dosing Diaries Entered, which is the number of dosing diaries with a YES confirming study drug dosing. [2] Only dosing diary records from date of first dose through date of Visit 4-1 will be considered for calculating secondary compliance to maintain the 28-

day treatment period.

[3] Compliance (%) based on Diary Entries = (Number of Dosing Diaries Entered) / (Number of Dosing Diaries Available) where Number of Dosing

Diaries Available is the total number of dosing diaries expected from a 28-day treatment (56 diaries).

Source: SDTM.XXXX or ADaM.XXXX

PROGRAM NAME: XXXXXXXXXX

Listing 16.2.6.1 WI-NRS Daily Ratings and Weekly Averages (Randomized Subjects)

| Subject ID | Treatment | Study Population | Week | Date (Study Day) of Rating | Daily Rating | Weekly Average | ≥4-Point Improvement | Any Improvement [1] |
|------------|--|--------------------------------|-------|-------------------------------|-----------------|-------------------|-------------------------|------------------------|
| xxxxx | N/A, B244 O.D. 5.0, B244 O.D. 20.0, Vehicle | N/A, Safety, mITT, PP | 1, 28 | DDMMMYYYY (xx) | xx | XX | Yes, No | Yes, No |

[1] Any improvement is defined as ≥ 1 point improvement from Baseline. Source: SDTM.XXXX or ADaM.XXXX PROGRAM NAME: XXXXXXXXX

Listing 16.2.6.2 AI-NRS Daily Ratings and Weekly Averages (Randomized Subjects)

| Subject ID | Treatment | Study Population | Week | Date (Study Day) of Rating | Daily Rating | Weekly Average | ≥4-Point Improvement | Any Improvement [1] |
|------------|--|--------------------------------|-------|-------------------------------|-----------------|-------------------|-------------------------|------------------------|
| xxxxx | N/A, B244 O.D. 5.0, B244 O.D. 20.0, Vehicle | N/A, Safety, mITT, PP | 1, 28 | DDMMMYYYY (xx) | xx | XX | Yes, No | Yes, No |

[1] Any improvement is defined as ≥ 1 point improvement from Baseline. Source: SDTM.XXXX or ADaM.XXXX PROGRAM NAME: XXXXXXXXX

Listing 16.2.6.3 POEM Items and Score (Randomized Subjects)

| Subject ID | Treatment | Study Population | Visit | Date of Rating | POEM Item | Rating [1,2] |
|------------|--|--------------------------------|---|----------------|---|--|
| XXXXXX | N/A, B244 O.D. 5.0, B244 O.D. 20.0, Vehicle | N/A, Safety, mITT, PP | Screening, Baseline, Week 2, Week 4, Week 8 | DDMMMYYYY | Days Skin was Itchy, Nights Sleep was Disturbed, Days Skin was Bleeding, Days Skin was Weeping or Oozing, Days Skin was Cracked, Days Skin was Flaking Off, Days Skin Felt Dry or Rough, Total Score | No days, 1-2 days, 3-4 days, 5-6 days, Every day, xxx (total score) |

[1] Numeric item conversion: No days=0; 1-2 days=1; 3-4 days=2; 5-6 days=3; Every day=4.
[2] Total score conversion: 0-2=Clear or almost clear; 3-7=Mild eczema; 8-16=Moderate eczema; 17-24=Severe eczema; 25-28=Very severe eczema.
Source: SDTM.XXXX or ADaM.XXXX

PROGRAM NAME: XXXXXXXXXX

Listing 16.2.6.4 5-D Pruritus Scale Items and Score (Randomized Subjects)

| Subject | | Study | | | | |
|---------|--|-------------|---------------------------------|----------------|--|--|
| ID | Treatment | Population | Visit | Date of Rating | 5-D Pruritus Scale Item [1] | Rating [1] |
| XXXXXX | N/A, | N/A, | Screening, | DDMMMYYYY | Duration: Hours per day Itching, | <6, 6-12, 12-18, 18-23, All Day |
| | B244 O.D. 5.0, B244 O.D. 20.0, Vehicle | mITT, PP | T, Week 2, Week 4, Week 8 | | Degree: Intensity of Itching, | Not Present, Mild, Moderate, Severe, Unbearable |
| | | | | | Direction: Itching Better or Worse, | Resolved, Much Better, Little Better, Unchanged, Worse |
| | | | | | Disability: Impact of Itching on Sleep, | Never, Occasionally, Frequent Delayed Sleep, Delayed Sleep and Occasional Night Waking, Delayed Sleep and Frequent Night Waking |
| | | | | | Disability: Impact of Itching on Leisure/School, | N/A, Never, Rarely, Occasionally, Frequently, Always |
| | | | | | Disability: Impact of Itching on Housework/Errands, | N/A, Never, Rarely, Occasionally, Frequently, Always |
| | | | | | Disability: Impact of Itching on Work/School, | N/A, Never, Rarely, Occasionally, Frequently, Always |
| | | | | | Distribution: Itching Present on Body Parts | Head/Scalp, Face, Chest, Abdomen, Back, Buttocks, Thighs, Lower Legs, Tops of Feet/Toes, Soles, Palms, Tops of Hands/Fingers, Forearms, Upper Arms, Points of Contact with Clothing, Groin |
| | | | | | Total Score | XXX |

[1] Duration, Degree, Direction, and Disability ratings use a 5-point Likert scale with responses rated from 1 (Low) to 5 (High). N/A ratings and Distribution ratings do not have a numeric equivalent. Source: SDTM.XXXX or ADaM.XXXX

PROGRAM NAME: XXXXXXXXXX

Listing 16.2.6.5 IGA (Randomized Subjects)

| Subject ID | Treatment | Study Population | Visit | Date of Rating | Rating [1] | Clear or Almost Clear | Any Improvement [2] | ≥2-Point Improvement to Clear or Almost Clear |
|------------|--|--------------------------------|---|----------------|---|-----------------------|---------------------|---|
| XXXXXX | N/A, B244 O.D. 5.0, B244 O.D. 20.0, Vehicle | N/A, Safety, mITT, PP | Screening, Baseline, Week 2, Week 4, Week 8 | DDMMMYYYY | Clear, Almost Clear, Mild, Moderate, Severe | Yes, No | Yes, No | Yes, No |

[1] Numeric item conversion: Clear=0; Almost Clear=1; Mild=2; Moderate=3; Severe=4.

[2] Any improvement is defined as \geq 1 point improvement from Baseline. Source: SDTM.XXXX or ADaM.XXXX

PROGRAM NAME: XXXXXXXXX

Listing 16.2.6.6 EASI Items and Score (Randomized Subjects)

| Subject ID | Tractmont | Study Bopulation | Visit | Data of Pating | Pody Area | EASI Itom | Dating [1] | Improvement |
|------------|-----------------|---------------------|------------|----------------|--------------------|---------------------|------------|--------------------|
| Subject ID | Treatment | Fopulation | VISIL | | Body Alea | EASI Itelli | | mprovement |
| XXXXXX | N/A, | N/A, | Screening, | DDMMMYYYY | Head/Neck, | Erythema | None, | Null if $< 50\%$, |
| | B244 O.D. 5.0, | Safety, | Baseline, | | Trunk, | Edema/Papulation | Mild, | ≥50%, |
| | B244 O.D. 20.0, | mITT, | Week 2, | | Upper Extremities, | Excoriation | Moderate, | ≥75% |
| | Vehicle | PP | Week 4, | | Lower Extremities, | Lichenification, | Severe, | ≥90% |
| | | | Week 8 | | | Area Score (%) [2], | xx-xx%, | |
| | | | | | Total | Total Score | XXX | |

[1] Numeric item conversion: None=0; Mild=1; Moderate=2; Severe=3.

[2] Numeric area score conversion: 1-9%=0; 10-29%=2; 30-49%=3; 50-69%=4; 70-89%=5; 90-100%=6.

Source: SDTM.XXXX or ADaM.XXXX

PROGRAM NAME: XXXXXXXXXX

DATE: HH:MM/DDMMMYYYY

Programming Notes:

• Body Area=Total corresponds to EASI Item=Total Score.

Listing 16.2.7.1 Adverse Events (Safety Population)

| Subject ID | Treatment | System Organ Class/ Preferred Term [1] | AE # | Start Date | End Date/Ongoing | Serious | SAE Criteria | Treatment Emergent | | |
|----------------------------------|---|---|------|------------|-----------------------|---------|--------------|-----------------------|--|--|
| XXXXXX | N/A, B244 O.D. 5.0, B244 O.D. 20.0, Vehicle | xxxxxxx/ xxxxxxxx | XXX | DDMMMYYYY | DDMMMYYYY, Ongoing | Yes, No | XXXXX | Yes. No | | |
| [1] MedDRA Dic Source: SDTM.X | [1] MedDRA Dictionary version XX.X was used to code adverse events. Source: SDTM.XXXX or ADaM.XXXX | | | | | | | | | |

PROGRAM NAME: XXXXXXXXXX

Listing 16.2.7.2 Adverse Event Details (Safety Population)

| | | System Organ Class/ | | | | | Led to Study |
|------------|-----------------|---------------------|------|-----------|-----------------|--------------------------|-----------------|
| Subject ID | Treatment | Preferred Term [1] | AE # | Severity | Relationship | Outcome | Discontinuation |
| XXXXXX | N/A, | xxxxxxx/ | XXX | Mild, | Definitely Not, | Recovered, | Yes, No |
| | B244 O.D. 5.0, | XXXXXXXX | | Moderate, | Unlikely, | Not Recovered, | |
| | B244 O.D. 20.0, | | | Severe | Possibly, | Recovered with Sequelae, | |
| | Vehicle | | | | Probably, | Fatal, | |
| | | | | | Definitely | Unknown | |
| | | | | | | | |

[1] MedDRA Dictionary version XX.X was used to code adverse events. Source: SDTM.XXXX or ADaM.XXXX PROGRAM NAME: XXXXXXXXX

Listing 16.2.7.3 Adverse Events for COVID-19 (Safety Population)

| | | System Organ Class/ | | | | | | Led to Study |
|------------|--|----------------------|------|------------|-----------------------|------------------------------|--|-----------------|
| Subject ID | Treatment | Preferred Term [1] | AE # | Start Date | End Date/Ongoing | Severity | Outcome | Discontinuation |
| XXXXXX | N/A, B244 O.D. 5.0, B244 O.D. 20.0, Vehicle | xxxxxxx/ xxxxxxxx | XXX | DDMMMYYYY | DDMMMYYYY, Ongoing | Mild, Moderate, Severe | Recovered, Not Recovered, Recovered with Sequelae, Fatal, Unknown | Yes. No |

[1] MedDRA Dictionary version XX.X was used to code adverse events. Source: SDTM.XXXX or ADaM.XXXX PROGRAM NAME: XXXXXXXXX

Listing 16.2.7.4 Deaths (Safety Population)

| Subject ID | Treatment | Date/Time of Last Dose | Date of Death | Related to Disease Under Study | AE Outcome=Fatal | AE # |
|-----------------------------------|--|------------------------|---------------|--------------------------------|------------------|----------|
| XXXXXX | N/A, B244 O.D. 5.0, B244 O.D. 20.0, Vehicle | DDMMMYYYY/HH:MM | DDMMMYYYY | Yes, No | Yes, No | |
| Source: SDTM.XXX PROGRAM NAME: | X or ADaM.XXXX XXXXXXXXXX | | | | DATE: HH:MM/DI | DMMMYYYY |

Listing 16.2.8.1 Hematology Parameters (Safety Population)

| Subject ID | Treatment | Visit | Date/Time of Lab Test | Lab Test | Result | Unit | Normality | Alert Flag [1] |
|------------|-----------------|------------|-----------------------|-----------------------|--------|------|-----------|----------------|
| XXXXXX | N/A, | Screening, | DDMMMYYYY/HH:MM | Basophils, | XXX | XXX | Normal, | LP, LN, N, HN, |
| | B244 O.D. 5.0, | Week 4, | | Basophils/Leukocytes, | | | Abnormal, | HP, AB, [Null] |
| | B244 O.D. 20.0, | Week 8 | | Eosinophils, | | | High, | |
| | Vehicle | | | Etc. | | | Low | |
| | v enitere | | | Liv. | | | LOW | |

[1] LP=Low Panic. LN=Low Normal. N=Normal. HN=High Normal. HP=High Panic. AB=Abnormal. [Null] when not used. Source: SDTM.XXXX or ADaM.XXXX PROGRAM NAME: XXXXXXXXX

Listing 16.2.8.2 Clinical Chemistry Parameters (Safety Population)

| Subject ID | Treatment | Visit | Date/Time of Lab Test | Lab Test | Result | Unit | Normality | Alert Flag [1] |
|------------|--|---------------------------------|-----------------------|---|--------|------|--------------------------------------|----------------------------------|
| xxxxxx | N/A, B244 O.D. 5.0, B244 O.D. 20.0, Vehicle | Screening, Week 4, Week 8 | DDMMMYYYY/HH:MM | Albumin, Alkaline Phosphatase, Alanine Aminotransferase, | XXX | xxx | Normal, Abnormal, High, Low | LP, LN, N, HN, HP, AB, [Null] |
| | | | | Etc. | | | | |

[1] LP=Low Panic. LN=Low Normal. N=Normal. HN=High Normal. HP=High Panic. AB=Abnormal. [Null] when not used. Source: SDTM.XXXX or ADaM.XXXX PROGRAM NAME: XXXXXXXXXX

Listing 16.2.8.3 Urinalysis Parameters (Safety Population)

| Subject ID | Treatment | Visit | Date/Time of Lab Test | Lab Test | Result | Unit | Normality | Alert Flag [1] |
|------------|-----------------|------------|-----------------------|------------|--------|------|-----------|----------------|
| XXXXXX | N/A, | Screening, | DDMMMYYYY/HH:MM | Bilirubin, | XXX | XXX | Normal, | LP, LN, N, HN, |
| | B244 O.D. 5.0, | Week 4, | | Clarity, | | | Abnormal, | HP, AB, [Null] |
| | B244 O.D. 20.0, | Week 8 | | Color, | | | High, | |
| | Vehicle | | | Etc. | | | Low | |

[1] LP=Low Panic. LN=Low Normal. N=Normal. HN=High Normal. HP=High Panic. AB=Abnormal. [Null] when not used. Source: SDTM.XXXX or ADaM.XXXX PROGRAM NAME: XXXXXXXXX

Listing 16.2.8.4 Urine Pregnancy Test (Safety Population)

| Subject ID | Treatment | Visit | Date/Time of Pregnancy Test | Result | Reason Not Done |
|--------------------------------|--|---------------------------------|-----------------------------|------------------------------------|---|
| XXXXXX | N/A, B244 O.D. 5.0, B244 O.D. 20.0, Vehicle | Screening, Week 4, Week 8 | DDMMMYYYY/HH:MM | Not Done, Positive, Negative | Subject is of non-childbearing potential, Subject is surgically sterile (for at-least one year), Subject is post-menopausal (for at-least one year), Other (specify) |
| Source: SDTM.XX PROGRAM NAM | XXX or ADaM.XXXX IE: XXXXXXXXXXX | | | | DATE: HH:MM/DDMMMYYYY |

Listing 16.2.8.5 Serology Parameters (Safety Population)

| Subject ID | Treatment | Visit | Date/Time of Lab Test | Lab Test | Result | Alert Flag [1] |
|------------------|--|------------------|------------------------------|---|--------------------------------------|----------------------------------|
| xxxxxx | N/A, B244 O.D. 5.0, B244 O.D. 20.0, Vehicle | Screening | DDMMMYYYY/HH:MM | Hepatitis B Virus Surface Antigen, Hepatitis C Virus Antibody, HIV-1/2 Antibody | Positive, Negative, Borderline | LP, LN, N, HN, HP, AB, [Null] |
| [1] I D-I ow Day | nie IN-Low Normal N | I-Normal HN-High | Normal HD-High Danie AB-Abno | rmal [Null] when not used | | |

[1] LP=Low Panic. LN=Low Normal. N=Normal. HN=High Normal. HP=High Panic. AB=Abnormal. [Null] when not used. Source: SDTM.XXXX or ADaM.XXXX PROGRAM NAME: XXXXXXXXX

Listing 16.2.9 Patient Reported Local Tolerability (Safety Population)

| Subject ID | Treatment | Day | Date of Rating | Symptom | Rating [1] |
|------------|-----------------|-------|----------------|-----------------------------------|------------|
| XXXXXX | N/A, | 1, 27 | DDMMMYYYY | Skin redness and/or color change, | None, |
| | B244 O.D. 5.0, | | | Itcning, | Mild, |
| | B244 O.D. 20.0, | | | Burning and/or stinging, | Moderate, |
| | Vehicle | | | Pain and/or tenderness, | Severe |
| | | | | New or changing rash | |
| | | | | | |

[1] Numeric item conversion: None=0; Mild=1; Moderate=2; Severe=3. Source: SDTM.XXXX or ADaM.XXXX PROGRAM NAME: XXXXXXXXX
Listing 16.2.10 Vital Signs (Safety Population)

| Subject ID | Treatment | Visit | Date/Time of Vital Signs | Vital Signs | Result | Unit | Normality [1] |
|------------|--|---|--------------------------|--|--------|------|---|
| XXXXXX | N/A, B244 O.D. 5.0, B244 O.D. 20.0, Vehicle | Screening, Baseline, Week 2, Week 4, Week 8 | DDMMMYYYY/HH:MM | Height, Weight, Body Mass Index (BMI), Body Surface Area (BSA), Systolic Blood Pressure, Diastolic Blood Pressure, Heart Rate, Respiratory Rate, Temperature | XXX | XXX | Normal, Abnormal NCS, Abnormal CS |

[1] NCS: Not Clinically Significant. CS: Clinically Significant. Source: SDTM.XXXX or ADaM.XXXX PROGRAM NAME: XXXXXXXXX

DATE: HH:MM/DDMMMYYYY

Listing 16.2.11 Physical Examination (Safety Population)

| Subject ID | Treatment | Visit | Date of Physical Exam | Body System | Result [1] | Description of Abnormality |
|------------|--|----------------------|-----------------------|--|---|----------------------------|
| XXXXXX | N/A, B244 O.D. 5.0, B244 O.D. 20.0, Vehicle | Screening, Week 8 | DDMMMYYYY | Cardiovascular, Dermatological, Ears, Extremities, Eyes, Gastrointestinal, General Appearance, Head, Lymph Nodes, Mouth/Throat/Neck, Musculoskeletal, Neurological, Nose, Respiratory, Thyroid | Normal, Abnormal NCS, Abnormal CS | XXXXXXX |

[1] NCS: Not Clinically Significant. CS: Clinically Significant. Source: SDTM.XXXX or ADaM.XXXX PROGRAM NAME: XXXXXXXXX

DATE: HH:MM/DDMMMYYYY

Listing 16.2.12 Smoking History (Safety Population)

| Subject ID | Treatment | Product | Smoking Start Date | Smoking End Date/ Ongoing | Packs per Day | Smoking Sessions per Week [1] |
|------------|--|---|--------------------|------------------------------|---------------|-------------------------------|
| XXXXXX | N/A, B244 O.D. 5.0, B244 O.D. 20.0, Vehicle | Tobacco Products, Non-Tobacco Products | DDMMMYYYY | DDMMMYYYY, Ongoing | XXX | XXX |

[1] A subject can have 4 smoking sessions per day (morning, afternoon, evening, and night). The number of smoking sessions per week = number of smoking sessions per day * 7. Thus, the maximum value for smoking sessions per week is 28. Source: SDTM.XXXX or ADaM.XXXX PROGRAM NAME: XXXXXXXXXX DATE: HH:MM/DDMMMYYYY

Listing 16.2.13.1 Prior and Concomitant Medications (Safety Population)

| Subject | Treatment | ATC Class Level 1/ Preferred Term [1] | CM# | Start Date | End Date/Ongoing | Indication | Dose | Unit | Frequency | Route | Prior Med [2] |
|---------|--|--|-----|------------|------------------|------------|------|------|-----------|-------|------------------|
| XXXXXX | N/A, | xxxxxxx/ | XXX | DDMMMYYYY | DDMMMYYYY, | XXX | XXX | xxx | xxx | XXX | Yes, |
